## Roles and Responsibilities

[name] will chair the Executive Committee for this project, serving as the Principal Investigator. The committee will also include Drs. [name] and [name] as co-Investigators. Each committee member is affiliated with the University of California, Los Angeles. The team will hold weekly teleconference calls. Monthly calls will include key investigators as needed. In these monthly meetings, we will address issues of data collection, budget, recruitment, treatment delivery, data management and analysis, and training and ongoing review to maintain interrater reliability. Also, we will discuss human subjects’ issues, especially the recruitment of BIPOC participants.

The Executive Committee will review all publications and presentations derived from data garnered in this grant in order to ensure its quality. Assignment of publications and other academic products of this project will be decided on by the Executive Committee. Disagreements will be resolved by majority decision. At the end of the trial, all publications and presentations derived from the data will be vetted within the Executive Committee prior to release.

## Specific Aims

Aim 1. Compare the differential effectiveness of the inhibitory retrieval model of exposure that emphasizes learning theory principles and a habituation-based model. Principal outcomes will include self-report and clinician rated symptoms. We hypothesize that the inhibitory retrieval model of exposure therapy will be more effective than the habituation-based model.

Aim 2. Examine the mechanisms of change in both the habituation and inhibitory-based treatment. We hypothesize that changes in associative learning in the inhibitory retrieval group (as indexed by self-report US expectancy and learning rate) will drive change in subsequent symptomatology and not the reverse. Additional examination of mechanisms will be exploratory.

Aim 3. Examine moderators and predictors of treatment in both the inhibitory and habituation-based models.

## Methods

### Trial Design

This will be an assessor-blinded, parallel, 2-arm, randomized (1:1) clinical superiority trial, for treatment-seeking adults with moderate to severe social anxiety or panic disorder.

### Participants

Participants will be recruited in the United States. A brief study description will be distributed via lab websites, social media, clinicaltrials.gov, and brochures to local agencies.

Inclusion criteria will consist of (1) Seeking treatment for social anxiety or panic disorder and demonstration of elevated scores (greater than two standard deviations of the normed mean) on standardized scales for anxiety (i.e., Mini SPIN or PDSS), (2) Age 18 to 65, (3) Either stabilized on psychotropic medications (1 month for benzodiazepines and beta blockers, 3 months for heterocyclics and SSRIs; self-reported) or medication-free (self-reported), (4) English-speaking, and (5) Clinical severity rating of 4 or higher on the Structured Clinical Interview for DSM-5 (SCID-5) for either panic disorder or social anxiety.

Exclusion criteria will consist of (1) Patient report of serious medical conditions – such as respiratory (e.g., chronic obstructive pulmonary disease), cardiovascular, pulmonary, neurological, muscular-skeletal diseases – or pregnancy, (2) History of suicidal ideation or self-harm in the past year; history of suicide attempts in the last 10 years, (3) History of bipolar disorder, psychosis, mental retardation or organic brain damage, (4) Substance abuse dependence within last 6 months, (5) Concurrent therapy focused on anxiety

Participants will be allowed to be in other forms of therapy, provided the therapy does not focus on anxiety (e.g., supportive counseling) and they have been stabilized on this alternative therapy for at least 6 months.

Interventions. Both interventions will entail 9 weekly exposure treatment sessions which are 60 minutes each, with the exception of first session which will be 90 minutes. Treatment sessions and laboratory assessments will be conducted at the UCLA Psychology Clinic and at UCLA's Anxiety and Depression Research Center laboratory.

Inhibitory Retrieval Condition (Experimental Comparator)

Participants will receive exposure therapy focused on maximizing extinction learning and expectancy violation. Participants will complete an OptEx Nexus to identify conditional stimuli (CS), unconditional stimuli (US), safety signals, and occasion setters. Exposures will be designed to “test out” if the US will occur. Consistent with associative learning principals, participants will conduct repeated exposure to the principal conditional stimulus (along with additional exposure to other CSs).

This condition includes techniques that incorporate associative learning principles such as deepened extinction, increasing attentional salience of the CS, variability in contexts and stimuli, occasional reinforcement, and mental reinstatement of extinction learning. Our manual is available to clinical researchers upon request.

Habituation Treatment (Active Comparator)

Participants will receive exposure therapy aimed at maximizing habituation and reducing fear responding. This condition includes techniques derived from the extant literature on habituation and dominant habituation models of exposure therapy. These include, but are not limited to, maintaining the exposure until fear declines, maintaining similarity across exposures, repetition of exposures until between session fear has declined, and a gradual approach to feared stimuli using an exposure hierarchy.

A list of feared situations will be generated and ranked in ascending order on the level of expected distress in that given situation (fear hierarchy). Treatment will begin with exposure to a moderately distressing stimulus (e.g., subjective units of distress or SUDS of 50-60) and continue through the individual's fear hierarchy towards the highest rated distressing situation. A given exposure will be focused on the given item on the fear hierarchy until initial SUDS has decreased by 50% or 45 minutes has passed. For example, if an individual reports that having a conversation with a stranger would elicit a distress rating of 80 out of 100, the individual would continue their exposure to this situation until they reach a distress rating of 40 or 45 minutes had passed. The same in-session exposure will be repeated between-session (consistent with models of habituation). Individuals will move up their fear hierarchy once between-session habituation (50% reduction in SUDS from the first exposure to this stimulus) has been achieved. Our manual is available to clinical researchers upon request.

Therapist Training, Supervision, and Fidelity

Therapists will consist of highly-trained graduate students. All graduate student therapists on the study will have been trained extensively by [name] and [name], both of whom have extensive experience in exposure therapy for anxiety disorders. All study therapists will attend an eight-hour workshop on exposure therapy from both an inhibitory retrieval and habituation perspective led by Drs. [name] and [name], as well as weekly supervision from Drs. [name] and [name]. All sessions will be audio- and videotaped for the purpose of supervision and fidelity ratings (i.e., checking of the degree to which therapists followed the prescribed treatment procedure).

## Outcome Measures

Principal and secondary outcome measures are depicted in Table 1.

**Table 1.** Self-report, behavioral, cognitive, and physiological measures at pre-treatment (week 0), weekly (sessions 1-9), mid-treatment (between week 4 and week 5), post-treatment (week 10) and at the 3-month follow up (week 24).

Week	Pre 0	Weekly (sessions 1-9)	Mid 4-5	Post 10	Follow-Up 24
Principal Outcome Measures					
S: Liebowitz Social Anxiety Scale- Self Report (LSAS-SR)	X		X	X	X
S: Panic Disorder Severity Scale-Self Report (PDSS-SR)	X	X	X	X	X
S: Clinician Severity Ratings (SCID-5)	X			X	X
Secondary Outcome Measures					
Mini-Social Phobia Inventory (Mini-SPIN)	X	X	X	X	X
Behavioral Approach Test (BAT)					
B: Duration of speech	X			X	
S: Subjective fear					
P: Heart rate					
S: Probability and Cost Questionnaire	X		X	X	X
S: Anxiety Sensitivity Index (ASI-3)	X		X	X	X
S: Positive and Negative Affect Schedule (PANAS-20)	X		X	X	X
S: Sheehan Disability Scale (SDS)	X		X	X	X
Fear Conditioning, Extinction, and Extinction Generalization Task					
C: Expectancy of unconditional stimuli	X			X	X
P: Heart rate, skin conductance					
Implicit Pavlovian Association					
C: Implicit associations for fear-relevant word stimuli	X		X	X	

B = Behavioral, C = Cognitive, P = Physiological, S = Subjective/experiential

### **Principal Outcome Measures.**

Self-reported symptom severity of social anxiety and panic disorder at pre-treatment, mid-treatment, post-treatment, and follow-up. Self-reported symptom severity of social anxiety disorder and panic disorder will be assessed using the Liebowitz Social Anxiety Scale-Self Report (LSAS; Baker et al., 2002) and Panic Disorder Severity Scale-Self Report (PDSS-SR; Houck et al., 2002), respectively.

The LSAS is a 24-item measure of social anxiety symptoms during the past week. The measure assesses the severity (0 = none, 3 = severe) and frequency (0 = never, 3 = usually) of social anxiety and social avoidance, with total sum scores ranging from 0 to 144. Higher scores indicate greater symptom severity and frequency. The LSAS demonstrates excellent internal consistency and correlational data corroborate its convergent validity (Baker et al., 2002).

The PDSS-SR is a self-report instrument adapted from the interviewer-administered Panic Disorder Severity Scale which assesses panic disorder symptom severity. This self-report measure assesses panic-related anxiety, distress, and avoidance in the past week.

Clinician-rated severity of social anxiety or panic disorder. Clinician severity rating (0-8) of social anxiety or panic disorder will be assessed using the Structured Clinical Interview for DSM-5 (SCID-5). The SCID is a semi-structured diagnostic interview, which will be completed by trained graduate students and reliability-checked by [name] or [name]. This interview (1) diagnoses anxiety disorders, mood disorders, somatoform disorders, and substance disorders; and (2) screens for psychosis. The results of the diagnostic evaluation will be presented at weekly meetings with the [name] or [name], who will check the diagnostic judgment and eligibility of the subject. Potential participants must receive a clinical severity rating of four or higher for their social anxiety or panic disorder in order to be eligible.

## **Secondary Outcome Measures.**

**Behavioral Avoidance Test (BAT).** Participants will complete a public speaking task in which they will speak for a short period of time in front of an audience while being videotaped. Participants will be assigned a topic from a randomized list and have one minute to prepare while seated. During this anticipation phase, we will measure their heart rate. Participants will then enter a room containing a video camera and three seated confederates. The floor will be lined with ten, equidistant markers between the camera and the wall, and participants will be told they can choose any marker to stand upon and deliver their speech. Markers will serve as a measure of approach and avoidance. Participants will then provide an initial SUDS rating (Subjective Units of Distress Scale (SUDS); where 0 = no fear and 100 = extreme fear) and begin speaking. Participants will provide SUDS ratings every minute during the 5-minute speech task and their heart rate will be measured during the speech.

Following the COVID-19 pandemic, the BAT consisted of a 5-minute recorded speech via Zoom with three confederates (and the experimenter) present. SUDS ratings were obtained as above but heart rate was not measured.

**Mini-Social Phobia Inventory (Mini-SPIN; Weeks et al., 2007)** The Mini-Social Phobia Inventory is a three-item self-report measure derived from the Social Phobia Inventory which screens for social anxiety. The Mini-SPIN shows high internal reliability and consistency across studies and correlational data support its convergent and discriminant validity (Weeks et al., 2007). The Mini-SPIN will be administered weekly, prior to each session as well as pre-treatment, mid-treatment, post-treatment and follow-up.

**The PDSS-SR** is a self-report instrument adapted from the interviewer-administered Panic Disorder Severity Scale which assesses panic disorder symptom severity. This self-report measure assesses panic-related anxiety, distress, and avoidance in the past week. The PDSS-SR will be administered weekly, prior to each session, as well as pre-treatment, mid-treatment, post-treatment and follow-up.

**Probability and Cost Questionnaire.** The LSAS was modified to include probability (0-100) and cost/perceived aversiveness (0-100) ratings for if rejection occurred in each of the situations listed in the LSAS

**Anxiety Sensitivity Index (ASI-3; Taylor et al., 2007).** The Anxiety Sensitivity Index is an 18-item self-report measure which measures somatic concerns, social concerns, cognitive concerns, as well as global anxiety sensitivity.

**Positive and Negative Schedule (PANAS 20-item; Crawford et al., 2004)** Positive and Negative Affective Schedule (PANAS) is a widely used measure comprised of 20-items assessing positive affect and negative affect. Self-rated levels of positive affect and negative affect will be assessed ("during the past week"). The PANAS has high internal consistency and temporal stability. Correlational data support its convergent and discriminant validity. Confirmatory factor analyses support the construct validity of the PANAS.

**Sheehan Disability Scale (SDS; Sheehan, 1983)** The SDS will be used to assess the degree of impairment in daily functioning in (a) work activities, (b) social life and leisure activities, and (c) family life and home responsibilities (0-10 point scales).

**Fear Conditioning, Extinction, Extinction Generalization.** Fear extinction and extinction generalization will be measured using a laboratory-based fear conditioning and extinction paradigm. This experimental task is designed to measure extinction, retention of extinction learning, and generalization of extinction learning to novel stimuli. Multi-element "insects" consisting of figures comprised of various geometric shapes will be used for conditional stimuli and generalization stimuli. Dependent measures will include trial-by-trial US expectancy ratings, EMG startle response, skin conductance, heart rate and self-report valence ratings. Day 1 will entail conditioning and fear extinction. Participants will return 24 hours later for a test of extinction retention and extinction generalization. Acquisition will consist of seven trials of CS1+, CS2+, and CS- (21 trials total). Following self-report ratings, extinction will entail eleven trials of CS1, GS2 (a generalization stimulus of CS2 that employs elements from CS2 as well as novel elements), and CS- (33 trials total). Day 2 will entail tests of extinction retention (two trials of CS1) as well as tests of generalization of extinction (two trials of CS2 as well as a new generalization stimulus; GS2).

Implicit Pavlovian Associations. The Implicit Pavlovian Association (IPA) paradigm is a novel modified priming task designed to measure Pavlovian associations. Participants will engage in a lexical decision task where they have to decide with the target word is a word or non-word. Prior to each target words, 50 ms primes will be presented. Target words entail combinations of US (e.g., for social anxiety words may include “rejection”, “judgement”, etc.), no-US words (e.g., “acceptance”, “liked”, etc.), neutral words (e.g., “dinner”, “cook”) and non-words. Primes will include CS related (“party”, “speech”, etc.) or neutral words (“groceries”). Various combinations of primes and targets will be presented in order to assess the strength of CS-US and CS-no US associations.

### Sample Size

We used G\*Power 3.1.9.2 with the F test family; ANOVA: Repeated measures, within-between interaction.  $p = .05$ , power = .8, two groups, two measures, correlation among measures = .5, nonsphericity correction = 1. The anticipated effect size is  $f = .165$  (equivalent to  $d = .33$ ), based on Wechsler, Kumpers, and Muhlberger (2019) meta-analysis comparing two forms of exposure therapy. Power analysis suggests we need a total N of 62 participants who complete the study. With an expected attrition of approximately 25%, our estimated enrollment sample size is  $n = 90$ .

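### The sample size enters f = .165 for d = .33, but in the interaction test used d = .33 is f = .0825, so power at 62 completers is about 25%, not 80%.

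*Combined protocol and SAP*

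**What the plan says.** The Sample Size section of the combined protocol and SAP names one G*Power procedure, "ANOVA: Repeated measures, within-between interaction". Its settings are alpha .05, power .8, "two groups, two measures, correlation among measures = .5" and a nonsphericity correction of 1. For the effect it says "The anticipated effect size is $f = .165$ (equivalent to $d = .33", taken from a meta-analysis that compared two forms of exposure therapy. The result is 62 completers, raised to 90 enrolled for about 25% attrition. No G*Power effect-size option is named.

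Trial Design calls this a superiority trial with 1:1 randomisation. Statistical Methods tests the principal outcomes by a Condition x Time interaction in a multilevel model, with the pre-treatment score as a covariate.

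**The concern.** Cohen's f is the standard deviation of the relevant effects across cells, divided by the within-cell SD. For two independent means d apart, those effects are ±d/2, so f = d/2. The procedure used here tests a different quantity: whether the arms change differently. Part of a difference that appears only at the second measure goes into the group main effect and part into the time main effect, so the interaction effects are half as large. Carrying f = d/2 into this procedure doubles the assumed effect.

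This is the plan's only sample-size justification. The comparator is an active exposure therapy, and a modest difference of .33 is the plan's own expectation. If 80% power for that difference stays on record, a null result is likely to be read as evidence against the superiority hypothesis, although the trial had a poor chance of detecting the effect.

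**Working it through.** **Inputs (Sample Size section).** k = 2 groups, m = 2 measures, correlation ρ = .5, nonsphericity correction 1, alpha .05, f = .165 stated as d = .33, N = 62 completers, 90 enrolled, 25% attrition.

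**Formula (G*Power default for this test).** λ = f²·N·m/(1−ρ), with (k−1)(m−1) = 1 and (N−k)(m−1) = N−2 degrees of freedom. Power comes from the noncentral F distribution.

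**Step 1: the plan's own figure.** With f = .165 and N = 62, λ = .165² × 62 × 2/.5 = 6.75 and power is 72.5%. Reaching 80% takes N = 75 (76 with equal arms), so 62 does not reproduce from the stated inputs. With three measures in place of two, power at 62 is 81.0%, so the run may have used three. This is a separate discrepancy.

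**Step 2: f for the interaction.** Take cell means of 0 and 0 in one arm, and 0 and d in the other. Removing row and column means leaves four interaction effects of ±d/4, so f = d/4 = .33/4 = .0825. Conversely, f = .165 means d = 4 × .165 = .66. An interaction f of .165 from differences of .33 would need the arms to differ by .33 in opposite directions at the two measures, which randomisation rules out in expectation.

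**Step 3: power for d = .33 (f = .0825).**

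| Completers | λ | Power |
|---|---|---|
| 62 | 1.69 | 24.8% |
| 67 (90 × .75 = 67.5) | 1.82 | 26.5% |
| 90 (no attrition) | 2.45 | 34.1% |

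80% power needs 291 completers, or 292 with equal arms. The d detectable with 80% power is 0.72 at 62 and 0.69 at 67.

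**Step 4: simulation.** With 31 per arm, a t test on change scores and 40,000 runs, d = .33 was detected in 25.1% and d = .66 in 72.3%.

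**Step 5: other readings, all for d = .33.**
- *d in units of the change-score SD.* That SD is √(2(1−ρ)) = 1 at ρ = .5, so nothing changes. On this scale power at 62 is 25% for any ρ.
- *Higher correlation, d in raw SD units (assumed, not in the plan).* ρ of .6, .7 and .8 gives 30%, 38% and 52% at 62.
- *A convention with λ = f²N.* Here f = d/2 = .165 is the correct entry, but λ = .165² × 62 = 1.69 and power is again 24.8%.
- *Three measures.* With equal baselines and a difference that reaches .33, f is .067 to .078 and power at 62 is 19–24%. If the three are mid-treatment, post-treatment and follow-up, with differences of .165, .33 and .33, f is .039 and power is 9%.
- *Baseline-adjusted comparison at one visit.* The residual SD is √(1−.5²) = .866. Power is 31% at 62, 34% at 67 and 43% at 90. The d detectable with 80% power at 67 is about 0.60.

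**The case against.** The strongest reply is that the meaning of d is assumed. The section gives f first and d in parentheses, and the cited meta-analysis is not available here. If an interaction f of .165 had been carried over and merely relabelled as d = 2f, the entry would be right and only the label would mislead. This cannot be excluded, but a standardised difference between two therapies is the natural reading of a meta-analytic d. Even on the relabelled reading, 62 completers give 72.5%, not 80%.

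The second reply is that the effect-size option is unstated, so whether f was mis-entered depends on the convention. That is true of the entry but not of the power, which is 24.8% under both conventions.

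The third is that the planned analysis is not the two-measure ANOVA. This stands in part: 25% describes the plan's own calculation at 62 completers. A linear Condition x Time slope over the four visits, under equal correlations of .5 and differences that start at zero and reach .33, has roughly 16–30% power at 62, depending on the pattern and time coding. The baseline-adjusted comparison has 31–43%. None approaches 80%.

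Finally, the documents do not say how a null result would be interpreted, so that consequence is inference.

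**Conclusion.** The concern holds. For the anticipated d = .33, the stated test has 24.8% power at 62 completers, 26.5% at 67 and 34.1% at 90, against the 80% claimed. This rests on d being the between-group difference at the second measure (equivalently, the difference in change), equal arms at baseline in expectation, and the plan's own ρ = .5 and alpha = .05. Under the alternatives checked for d = .33 at 62 completers, power ranges from 9% to 52%, and baseline adjustment with all 90 completing gives 43%. The conclusion therefore does not depend on the exact reading of the design. The correction must be made because the error overstates the plan's headline power about threefold.

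**What to change.** Correct the Sample Size section in one of two ways.

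- Keep f = .165 and say that in this test it is a difference in change of d = .66. In that case also correct the N, because 80% power at that effect needs 75 completers (76 with equal arms), and 62 gives 72.5%.
- Enter f = .0825 and report about 25–27% power for d = .33 at 62–67 completers.

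In either case, name the effect-size convention and the number of measures used. State the effect detectable with 80% power at the planned size (d about 0.69–0.72). For the baseline-adjusted post-treatment comparison, report about 31–34% power at d = .33 and a detectable d of about 0.60 at 67 completers. Say that ρ = .5 is assumed, and present the trial on that basis.

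The cost is wording in one section and a much less favourable power statement. Enrolment, conduct and the analysis do not change.

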### Statistical Methods

In order to examine the principal outcomes, we will use multilevel modeling Stata 17.0 to test a Condition x Time interaction in predicting normalized symptom scores. We will use repeated measures as a Level 1 factor and Condition as a Level 2 factor. Condition will be included as a categorical variable (Inhibitory, Habituation). For the principal analyses (LSAS and PDSS at pre-treatment, mid-treatment, post-treatment, and follow-up), Time will be included as a continuous variable. We will then follow-up with models using Time as a categorical variable involving three time-points (mid-treatment, post-treatment, 3-month follow-up) to examine differences at specific time points (post-treatment and follow-up) while simultaneously examining potential differences in the slopes of

the inhibitory retrieval and habituation condition from mid-treatment to post-treatment and post-treatment to follow-up. Similar models will be run for secondary outcomes (e.g., weekly Mini-SPIN, weekly PDSS, and BAT). Pre-treatment normalized symptom scores will be included as a covariate. As we conducted exposure therapy both in-person and remotely (due to COVID-19), we will also include Remote Therapy as a categorical factor (in-person, remote) in the models.

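### The inputs printed in the sample-size paragraph require 76 completers, not 62; at 62 they give about 72.5% power, not 80%

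*Combined protocol and SAP*

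**What the plan says.** The Sample Size section specifies G*Power 3.1.9.2, F tests, repeated-measures ANOVA with a within-between interaction, at alpha .05 and power .8. The remaining settings are "two groups, two measures, correlation among measures = .5, nonsphericity correction = 1", with an anticipated f of .165. It then states: "Power analysis suggests we need a total N of 62 participants who complete the study". The enrolment figure follows: "With an expected attrition of approximately 25%, our estimated enrollment sample size is" 90. Randomization and Masking gives 1:1 allocation.

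The section does not say which visits the two measures are. Under Statistical Methods the principal analysis has four visits ("LSAS and PDSS at pre-treatment, mid-treatment, post-treatment, and follow-up), Time will be included as a continuous variable"), followed by "models using Time as a categorical variable involving three time-points (mid-treatment, post-treatment, 3-month follow-up"). Baseline also enters as an adjustment term: "Pre-treatment normalized symptom scores will be included as a covariate". In Table 1 of Outcome Measures, the third principal outcome ("S: Clinician Severity Ratings (SCID-5")) is taken at pre-treatment, post-treatment and follow-up.

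**The concern.** The paragraph gives everything needed to repeat the calculation, so 62 should come back exactly. It does not, and no other section corrects it. This paragraph is the only justification of sample size in a superiority trial, and the enrolment target is built on the 62.

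If the printed inputs are what was entered, the chance of missing the planned effect with 62 completers is about 27.5% rather than 20%, which matters when a null result is interpreted. If a different input was entered, the design may have been adequate and the paragraph misdescribes it. A reader cannot tell which. The point takes f = .165 as printed, so it does not depend on how that effect size was obtained.

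**Working it through.** **Inputs, all from Sample Size except allocation.** f = .165, alpha = .05, target power .80, groups k = 2, measures m = 2, correlation rho = .5, nonsphericity epsilon = 1. Allocation is 1:1, so N is even.

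**Formula** (standard G*Power effect-size convention for this procedure). With epsilon = 1:

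- lambda = f² × N × m / (1 − rho)
- df1 = (k − 1)(m − 1); df2 = (N − k)(m − 1)
- power = P(noncentral F(df1, df2, lambda) > F critical at .95)

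**The plan's own figure, N = 62.** f² = .027225, so lambda = .027225 × 62 × 2 / .5 = 6.752. With df 1 and 60, the critical F is 4.001 and power is **.7246**.

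**N required with the printed inputs (m = 2).**

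| N | lambda | power |
|---|---|---|
| 62 | 6.752 | .7246 |
| 67 | 7.296 | .7584 |
| 68 | 7.405 | .7647 |
| 74 | 8.059 | .7998 |
| 75 | 8.168 | .8051 |
| 76 | 8.276 | .8104 |

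The minimum is 75, or **76** with equal arms (38 each). That is 14 more than stated.

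**Cross-check on change scores.** In a 2 × 2 layout, f = .165 is a between-arm difference in change of 4 × .165 = .66 SD. With rho = .5 the SD of change is √(2 × (1 − .5)) = 1. The squared noncentrality of the t-test is then .66² × 62/4 = 6.752, the same lambda. A simulation of that t-test (200,000 runs) gave .726 at 31 per arm and .810 at 38 per arm.

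**Could another convention give 62?** Keeping the printed values:

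- within-factor test, one group: 75
- between-factor test: 220
- lambda = f²N convention: 292
- two-sample comparison at d = .33: 290

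One-sided alpha gives 60 and rho = .6 gives 60. Both contradict the printed settings.

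**Which single change returns 62 with equal arms** (power below .80 at 60 and at least .80 at 62)?

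| Changed input | Value | Power at 60 | Power at 62 |
|---|---|---|---|
| Measures | 3 | .7963 | .8103 |
| f (m = 2) | about .181 to .183; e.g. .1825 | .7940 | .8072 |
| rho (m = 2) | about .584 to .597; e.g. .59 | .7927 | .8060 |

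Four measures gives 52, not 62.

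**Enrolment.** 90 × .75 = 67.5, so 67 or 68 completers. For 62 completers, 62/.75 = 82.7, so 83 enrolled; 90 is a conservative margin if 62 is right. For 76 completers, 76/.75 = 101.3, so 102 enrolled.

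**Power at 67 or 68 completers.** Printed inputs: 75.8% to 76.5%. Three measures: 84.2% to 84.8%.

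**Effect detectable with 80% power (printed inputs).** f = .181 at 62 completers and .172 to .174 at 67 or 68, against the planned .165.

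**The case against.** The arithmetic is not in dispute; the objections concern its weight.

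- **A shortfall is not proven.** The same procedure with three measures returns exactly 62, and Statistical Methods contains a model with three time points, so a misprinted number of measures beside a correct N is plausible. This stands as a possibility, and it is why the 72.5% must be read as conditional on the printed inputs. It does not settle the matter. The three-point model is only a follow-up to a four-visit model, the clinician rating has three occasions (two if baseline is a covariate), and the other substitutions also return 62. On this reading the paragraph is still wrong as printed.
- **The plan enrols 90, not 62.** With 25% attrition, power under the printed inputs is about 76%, some 4 points under target. The 72.5% applies only if completers fall to 62, which is 28/90 = 31% attrition. This is fair and narrows the practical gap without closing it.
- **The planning ANOVA is not the analysis.** The principal analysis is a multilevel model on four visits. A four-measure ANOVA would give power of .877 at 62, but it does not reproduce 62, and the principal model treats time as continuous. The power of that model is a separate question.
- **Nothing is biased.** True: neither the effect estimate nor the test is affected. The error is in the figure that justifies the sample size.

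**Conclusion.** The concern holds. The stated 62 completers for 80% power is contradicted by the inputs printed beside it, which require 76 and give 72.5% power at 62 (75.8% to 76.5% at 67 or 68). Established: at least one of the printed inputs, or the 62, is wrong. Not established: which one, and hence whether the trial is underpowered against its own target. Three measures is the simplest single change that matches, but that is an inference. If it is right, power is 81.0% at 62 and 84.2% to 84.8% at 67 or 68, and there is no shortfall.

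These figures accept f = .165 as printed, use the standard G*Power effect-size convention and equal arms, and describe the planning ANOVA only, not the multilevel model.

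**What to change.** Check the saved G*Power run or repeat it, list every input as entered, and correct whichever figure differs:

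- **If the printed inputs were used:** state that 80% power needs 76 completers, and that power is about 72% at 62 and about 76% at the 67 or 68 expected from 90 enrolled.
- **If three measures were entered:** change two measures to three and keep 62, with power of 81% (about 84% to 85% at 67 or 68).
- **If f or the correlation was entered differently:** print the value used and its basis.

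In each case, keep the 25% attrition assumption and either state the 67 or 68 completers that 90 yields or explain the margin over 83. It would also help to name the visits that the measures represent and to say that this is an ANOVA approximation rather than the power of the multilevel model.

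The cost is one re-run and one corrected paragraph, with no change to enrolment, estimand or analysis. Stated power falls by about 4 to 8 points if the printed inputs are right. It does not fall if a different input was entered and can be justified.
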